## **28.0 Data and Specimen Management\***

**Data Management:** Data will include that obtained from the study surveys and medical record, as described above.

Data will be collected via REDCap or paper survey or EHR review. Data from the surveys and EHR will be stored in REDCap. Paper surveys, if used in the event of a REDCap or other IT issue, will be stored in a locked office of the investigators.

Deidentified data will be exported from REDCap to statistical programs for analysis (e.g., SAS, SPSS, Excel). All data will be securely stored on password-protected CM servers.

Strict measures will be taken to ensure participant privacy and confidentiality. Participants will be assigned a unique study identification number. Additionally, survey data will be collected using a unique, participant-created code such that a link between participant survey number and participant identity do not need to be linked. The study REDCap project will be set up such that the study team will not be able to link survey data to individual participant identity. All personally identifiable information needed to facilitate data collection and intervention fidelity review will be kept strictly confidential, stored on REDCap, and accessible only to designated study team members. Only study team members needing access to data to fulfill their study responsibilities will have access to the data. Non-study team members will not have access to the data.

Data will be stored per CM records retention policy.

**28.1 Specimen Management:** *Describe how specimens will be handled, including:*

SHORT TITLE:

Genetic data and biospecimens will be stored up to 5 years for this study (IRB STUDY00002116); biospecimen storage will occur in the existing Adolescent Medicine Pharmacogenetic Repository.

*If this study involves storing of data or banking of leftover specimens for future research, indicate how the use will be managed:*

- Contributing data and/or leftover specimens to an existing CM repository protocol (myIRB# \_\_\_\_\_)
- Contributing data and/or leftover specimens to an existing non-CM repository (Institution/Repository Name: \_\_\_\_\_)
- Not contributing to an existing repository for the management of data/specimens for future research use.
- Other: Samples will be stored in the Adolescent Medicine Pharmacogenomic Repository (AMP) (IRB#13020033).

Saliva or salvaged blood samples will be stored in the AMP freezer space until time of analysis. The samples will be accessed by study team members and lab members needed to analyze the samples. All personnel are CM researchers. All samples will be deidentified and marked in with a systematic record number including no individual identifying information.

For participants who begin the study as a minor and turn 18 they will be asked to reconsent at a subsequent study interaction which will provide written consent using eConsent.

### **30.0 Provisions to Monitor the Data to Ensure the Safety of Subjects**

Although this study represents no more than minimal risk to participants, we will exercise the following provisions to ensure participant safety. *[name] will have overall responsibility for monitoring the safety of participants and data. The data and safety monitoring plan will be developed in accordance with NIH guidelines and code of federal regulations established by the Department of Health and Human Services (45 CFR 46; the Common Rule). [name] will share reports of preliminary data with [name] (primary mentor) monthly through the duration of participant enrollment and data collection. In the unlikely event of an adverse outcome associated with the study protocol, the outcome will be documented and, as appropriate, reported to the Institutional Review Board, FDA and NIH.*

#### ***Regulatory Requirements & Site Performance***

SHORT TITLE:

*This multi-site collaborative research study (see below under Multi-Site Research) is approved by the CMKC Institutional Review Board (IRB) and will comply with all applicable regulatory requirements. The committee will monitor subject accrual and retention and ensure that the study cohort is balanced for age, gender, race/ethnicity.*

**Monitoring Committee** A Data Safety Monitoring Board (DSMB) will be established, to periodically review and evaluate accumulated study data for participant safety, study conduct and progress, and efficacy. Based on these assessments, the DMSB will make recommendations regarding the continuation, modification, or early termination of the study. The committee will meet twice yearly (via teleconference) to review the studies associated with this application and to monitor any adverse events. Documentation of the meetings will be recorded and stored in the Division of Pediatric Hospital Medicine at CMKC. The DMSB membership will include experts in adolescent health and tobacco use and investigators with expertise in the conduct and methodology of trials for behavioral interventions. Members of the DSMB will review the written protocols, informed consent procedures, and plans for data and safety monitoring. The DSMB reporting guidelines will then be individualized for the study, taking into consideration the population under study, the known or anticipated adverse outcomes or risks of the study procedures, and any other data monitoring or oversight required. The DSMB will review data quality and timeliness, adherence to the study protocol, participant recruitment and consenting procedures, accrual and retention figures, and all adverse and other events and outcomes. For the purposes of DSMB review, adverse and other events will be defined broadly to include any negative occurrence experienced by a participant during the course of their participation in the study regardless of any investigator-determined attribution to the study protocol or procedure. This allows the DSMB to independently evaluate attribution for the event. Through these reviews the DSMB determines whether cumulative data indicate the need to change the research design, to modify information presented to participants, or to terminate the project. New scientific developments outside the study that may impact participant safety or the ethics of the study are considered in making these determinations. Pre-specified stopping rules are established in consultation with the investigator and are employed if significant benefits or risks have developed, if trial management issues prevent successful completion, or if compelling ethical concerns arise. Again, should it be deemed necessary to have a DSMB, we will elucidate the plan in greater detail in accordance with institutional guidelines.

**30.1** *In addition to the Principal Investigator, which individual or group will be responsible for monitoring the data and safety for this study?*

Sponsor or Sponsor Designee (including the Sponsor CRO)

SHORT TITLE:

- Data and Safety Monitoring Board (DSMB) or Data Safety Monitoring Committee (DSMC)
- Independent Monitor (s)
- Internal Committee at CM
- Other: \_\_\_\_\_

**30.2 Data Safety Monitoring Plan:** Please see Data Safety and Monitoring plan in IRB documents for details.

## STUDY MANAGEMENT

### 31.0 Setting & Locations\*

**31.1** *Describe the sites or locations where the research will be conducted.*

- *Identify where research procedures will be performed including any non-CM affiliated locations. For any non-CM affiliated locations, upload a letter of support in myIRB which states that the site is aware that research will be conducted on their premises.*
- *Describe the composition and involvement of any community advisory board.*
- *For research conducted outside of CM and its affiliates describe:*
  - *Regulations or customs affecting the research*
  - *The local scientific and ethical review structure*
- *Describe the availability of medical or psychological resources that subjects might need as a result of taking part in the study.*

### 32.0 Multi-Site Research

Is this a multi-site or collaborative research study?

No      If no, you do not need to complete this section.

Yes      If yes, continue below:

**Multi-Site Research:** *Multiple sites will be engaged in this human research project. Sites will use the same protocol to conduct the same human research activities (except for minor variations due to local context considerations).*

**Collaborative Research:** *Multiple sites will be engaged in this human research project. Sites will not be performing the same research activities. The Site submission will specify the specific research activities each site will perform.*

**REQUIRED:** *Enter summary of site-specific activities that differ from the overall protocol:* The study P.I. [name] MPH, will start a

SHORT TITLE:

new position at Children's Hospital of Los Angeles (CHLA) on November 1, 2024. At that time we will assign a new CMH site PI ([name], currently co-Investigator) and [name] will be added as an external collaborator at CHLA with a external reliance on CMH IRB. No study participants will be enrolled at CHLA but data containing PHI will be shared with [name] and necessary study team members at CHLA for data analysis and dissemination (manuscript and future grant preparation).

**Student(s):** Student(s) will help with this project and will be engaging their home institution.

**Visiting Resident(s) / Visiting Fellow(s):** Visiting Resident(s) / Visiting Fellow(s) will help with this project and will be engaging their home institution.

**Is Children's Mercy (CM) acting as the single IRB of Record (sIRB)?**

**No, each site is getting their own IRB approval.**

**Yes, some or all sites will rely on the CM as the sIRB.**

- **Reliance is required for non-Exempt NIH or other Federally Funded research where:**
  - *The institution's employees or agents intervene or interact with human subjects for research purposes;*
  - *The institution's employees or agents obtain individually identifiable private information or identifiable biospecimens about human subjects for research purposes; or*
  - *The institution receives a direct HHS award to conduct human subjects research, even where all activities involving human subjects are carried out by a subcontractor or collaborator.*

**If CM is sIRB for another site, complete the chart for that site(s) (Add a new row for each site relying on the CM IRB, delete chart if not acting as sIRB):**

Site Name	Enrollment Goal for Site(s) Choose One	Relying on CM IRB?
CHLA	 Site Enrollment Goal: N/A   Site will not enroll: No study subjects will be	 External Site will rely on the CM IRB as the IRB of Record using a reliance agreement.   Not Applicable. Site will not interact or intervene with human participants or their identifiable data / identifiable biospecimens.

SHORT TITLE:

	enrolled, however data containing PHI will be shared with this study site for analysis.	Site is also not a primary NIH or federal grant recipient.

**32.1 Multi-Site Research:**

All study procedures will occur at CMH. However, some co-investigators are from non-CM institutions: [name] MD MPH (University of Rochester Medical Center, Rochester NY), [name] (University of Kansas Medical Center). These study members are categorized as not participating in human participants research as they will at no time interact with study participants or have access to identifiable data. The study P.I. [name] MPH, will start a new position at Children's Hospital of Los Angeles (CHLA) on November 1, 2024. At that time we will assign a new CMH site PI ([name], currently co-Investigator) and [name] will be added as an external collaborator at CHLA with a external reliance on CMH IRB. No study participants will be enrolled at CHLA but data containing PHI will be shared with [name] and necessary study team members at CHLA for data analysis and dissemination (manuscript and future grant preparation).

Title: Development and Implementation of a Tobacco and ENDS Treatment Intervention for Adolescents and Young Adults in the Pediatric Hospital

Clinical Trial: NCT05936099

Date: August 30 2024

STATISTICAL DESIGN AND POWER

Aim 2: Evaluate preliminary efficacy and implementation outcomes of our tobacco and ENDS use intervention

Design: We will conduct a prospective, pilot trial with 3-month follow up to assess preliminary efficacy and implementation outcomes (Table 3). Hospitalized AYAs (n=144) with current (past 30-day) ENDS use (including those with co-use of cigarettes) will be randomized 2:1 to receive our novel intervention or control intervention that will consist of brief advice and printed quit line referral (see Figure 2). We will evaluate preliminary efficacy (i.e., 30-day self-reported abstinence with biochemical verification) as the primary outcome. We will also assess self-reported motivation and confidence to quit immediately post-intervention and at 3-month follow up and implementation outcomes (i.e. acceptability, feasibility, and fidelity).

Data Sources: AYAs: surveys, electronic health record; Parents/Guardians: surveys; Hospital Provider (i.e., [name]: survey, audio-recording of sessions; Health educator: survey, field notes, audio-recording of sessions

Assessments:

AYA Participants: We will use confidential, web-based surveys administered via Research Electronic Data Capture (REDCap) to capture AYA data pre- and post-intervention, 3-month follow up (Research Strategy Table 3 and 4, Appendix). The health educator will recruit, screen, consent, and randomize eligible participants. AYAs who decline to participate will be asked to provide age, sex, race and ethnicity to facilitate identification of participation bias. Randomization of consented participants will be stratified on sex and age using a 2:1 ratio within strata via computer generated assignment sequence placed in sequentially numbered sealed envelopes. *Control participants* will receive brief advice from the health educator regarding tobacco and ENDS use cessation and printed referral to a quit line. *Intervention participants* will receive the intervention developed in Aim 1, administered by the same health educator and [name]. All participants will complete a pre- and post-intervention survey and a 3-month survey sent via email, text message, and/or mailed paper survey so the research team is not directly involved in outcome data collection.

Parents/guardians of AYAs will be asked to complete a post-intervention survey. The health educator will complete brief survey items and field notes after each session. The AYA intervention and control sessions will be audio-recorded and reviewed by Drs. [name] and [name] to assess fidelity and provide feedback. [name] will review audio-recordings of [name] sessions (e.g., Assist: NRT prescription) to assess fidelity and give feedback.

Participant demographics and clinical characteristics (e.g., age of initiation, nicotine dependence) will be assessed at baseline. The outcome measures, method of assessment, relevant stakeholders and detailed description are depicted in Table 3 and sample survey items in Table 4. *Preliminary efficacy* will be assessed via self-reported 30-day point prevalence tobacco/ENDS abstinence using the timeline follow-back method at 3-month follow-up.⁷³ To obtain a biochemically verified outcome and to encourage accurate self-reporting we will assess salivary cotinine via mailed samples from all participants (not currently on NRT) who report abstinence. Although accurate verification will not be possible with participants who are occasional users or using NRT, this will also allow us to evaluate the feasibility of collecting saliva by mail in this population which will be informative for future studies with daily ENDS users. Secondary efficacy outcomes will include *self-reported motivation and confidence to quit immediately post-intervention and at 3-month follow up*.^{65, 74,75} We will assess *acceptability* with the overall intervention and intervention components via *survey* immediately post intervention (AYAs and parents) and at 3 month follow-up (AYAs). Acceptability will also be evaluated via participant *enrollment and session completion rates*. *Feasibility* will be assessed via *intervention duration* in minutes from audio recordings and [name] and the health educator will complete a brief survey and record field notes to assess feasibility (e.g., *impact on workflow, disruption, suitability*). To assess *fidelity* we will *review audio recordings* and rate health educator intervention and control sessions based on a previously developed fidelity rating scales.

AYA participants: We will use confidential, web-based surveys administered via Research Electronic Data Capture (REDCap) to assess post-intervention outcome measures including preliminary efficacy using previously validated survey questions to assess self reported 30-day abstinence and acceptability using 5-point

Parents/Guardians: We will use confidential, web-based surveys administered via Research Electronic Data Capture (REDCap) to assess post-intervention 5-point Likert scale implementation items among parents/guardians of AYA participants (Research Strategy Tables 3 and 4, Appendix).

Hospital Provider ([name]): We will use confidential, web-based surveys administered via REDCap to assess post-intervention 5-point Likert scale items and audio-recording of sessions to examine feasibility and fidelity (Research Strategy Table 3 and 4, Appendix).

Health Educator: We will use confidential, web-based surveys administered via REDCap to assess post-intervention 5-point Likert scale implementation items and will take field notes (Table 3 Research Strategy, Appendix). We will use field notes, audio-recording of sessions and survey items by the health educator to examine feasibility and fidelity.

Analysis:

We will use level of significance $\alpha=0.05$ and all analyses will be conducted using SAS v 9.4 (SAS Institute, Cary, NC, USA).

Measures and Statistical Analysis:

Participant demographics and clinical characteristics (e.g., age of initiation, nicotine dependence) will be assessed at baseline. The outcome measures, method of assessment, relevant stakeholders and associated outcome measures are depicted in Table 3 and sample survey items in Table 4.

To assess *preliminary efficacy*, differences in self-reported and biochemically verified 30-day tobacco/ENDS use abstinence at 3-month follow up (primary outcome) will be analyzed using a generalized linear model assuming an underlying binomial distribution and logit link function to compare between study arms. Motivation and Confidence to quit will be analyzed using a repeated measures analysis of variance. Potential differential outcomes based on sex and demographic factors will be explored. Chi-square (categorical variables) and Wilcoxon Rank Sum (continuous variables) tests will be used to assess participation bias. For acceptability, we will calculate the proportion of AYA participants and parents/guardians in the intervention arm with mean ratings of satisfaction and acceptability of ≥ 4 on the 5-point Likert scale. In addition, frequencies and percentages will be used to describe the enrollment and session completion rate. For *feasibility* we will conduct thematic analysis of field notes and conduct simple descriptive analyses (means, frequencies, percentages) of the brief survey items completed by [name] and the health educator and session length data. *Fidelity* will be summarized utilizing similar descriptive analyses of the fidelity ratings (e.g., percentage of intervention steps completed; mean rating of key MI skill adherence). Potential differential outcomes based on sex and demographic factors will be explored. Chi-square (categorical variables) and Wilcoxon Rank Sum (continuous variables) tests will be used to assess participation bias.

Sample Size Our proposed *sample size* [$n=144$ (96 treatment, 48 control)] is well within the recommendations for behavioral intervention development pilot trials based on what is feasible to recruit in our hospital and judged to be sufficient to evaluate efficacy (i.e., self-reported/biochemically verified abstinence) in a preliminary behavioral design trial.^{63,64} With respect to percentage reporting self-reported and/or biochemically confirmed abstinence at 3-mo follow up the margin of error (ME) around our observed outcomes depends on the observed proportion with the largest ME occurring when the proportion is 50%. Our sample size is sufficient to provide a ME of 10% (if the proportion is 50%) or less. A study fully powered to determine efficacy will be the focus of an R01 hybrid implementation trial informed by this study.

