### 2.0 Objectives\*

#### 2.1 Purpose, specific aims or objectives:

**Design and iteratively refine a tobacco and ENDS use intervention for AYAs.** We will draw on promising primary care and hospital-based approaches to develop and iteratively refine, based on survey and interviews of key stakeholders, a novel intervention to screen for and treat current tobacco and ENDS use in hospitalized AYAs.

**Evaluate preliminary efficacy and implementation outcomes of the tobacco and ENDS use intervention.** We will conduct a randomized pilot trial with 3-month follow up to assess preliminary efficacy and implementation of the intervention in hospitalized AYAs with current tobacco and ENDS use. Self-reported 30-day abstinence with biochemical verification at 3 months will be the primary outcome and secondary outcomes will include implementation measures (e.g., acceptability, feasibility, fidelity).

**Exploratory secondary aim:** We will explore the impact of individual-level factors (e.g., CYP2A6 genotype, nicotine metabolite ratio, sex) at baseline with our primary outcome (past 30 day ENDS use abstinence).

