## **2.2 Hypothesis to be tested/Exploratory study design:**

We hypothesize the intervention arm will have higher rates of biochemically confirmed self-reported tobacco use abstinence (preliminary efficacy; primary outcome) compared to the control arm at 3 month follow up.

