
CYP2A6 genotype-predicted phenotype (slow, intermediate, extensive) and other genetic variants of interest may be explored as co-variants in the analysis. Given the exploratory nature of the genetic analysis, we are likely underpowered to find significant association across numerous genetic co-variants, but these data may inform future studies designed to evaluate the relationship.

SHORT TITLE:

**27.2** Our proposed sample size [n=144 (96 treatment, 48 control)] is well within the recommendations for behavioral intervention development pilot trials based on what is feasible to recruit in our hospital and judged to be sufficient to evaluate efficacy (i.e., self-reported/biochemically verified abstinence) in a preliminary behavioral design trial. With respect to percentage reporting self-reported and/or biochemically confirmed abstinence at 3-mo follow up the margin of error (ME) around our observed outcomes depends on the observed proportion with the largest ME occurring when the proportion is 50%. Our sample size is sufficient to provide a ME of 10% (if the proportion is 50%) or less.

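### The primary logistic model is stated as an arm comparison only; adjusting for the sex and age strata and baseline nicotine dependence would be a small, nearly free gain in efficiency

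*SAP*

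**What the plan says.** The primary analysis is given in one sentence, the same in the SAP (Measures and Statistical Analysis) and Protocol 27.1: the abstinence outcome "will be analyzed using a generalized linear model assuming an underlying binomial distribution and logit link function to compare between study arms". Arm is the only term named.

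The design and data collection supply three further baseline variables:

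- **Strata.** "Randomization of consented participants will be stratified on sex and age using a 2:1 ratio within strata" (SAP, Assessments; also Protocol 5.1 and 8.3).
- **Dependence.** "Participant demographics and clinical characteristics (e.g., age of initiation, nicotine dependence) will be assessed at baseline" (SAP, Measures and Statistical Analysis; also Protocol 5.1, 9.0 and 27.1).

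Neither document brings these into the primary model. The nearest statements do something else:

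- SAP, Measures and Statistical Analysis: "Potential differential outcomes based on sex and demographic factors will be explored". This concerns differences in outcome between subgroups, not adjustment of the arm comparison.
- Protocol 2.1, exploratory aim: "We will explore the impact of individual-level factors (e.g., CYP2A6 genotype, nicotine metabolite ratio, sex) at baseline with our primary outcome".
- Protocol 27.1: "CYP2A6 genotype-predicted phenotype (slow, intermediate, extensive) and other genetic variants of interest may be explored as co-variants in the analysis". These are the only covariates named anywhere, and they are genetic, optional and exploratory.

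The plan does intend a between-arm comparison. Protocol 2.2 says "We hypothesize the intervention arm will have higher rates of biochemically confirmed self-reported tobacco use abstinence" than control, and the SAP sets alpha at 0.05 ("We will use level of significance" opens that sentence).

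**The concern.** When randomisation is stratified on factors that predict the outcome, the arms are balanced on them by design. A model that omits them still counts their variation as noise. Omitting a prognostic baseline score also gives up precision that the score could have supplied. With 48 controls the comparison is imprecise to begin with, and the SAP's Sample Size paragraph says the study will inform a later, fully powered trial. At stake are a few points of power and a slightly narrower interval, obtainable from data the trial already collects.

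**Working it through.** **Inputs from the documents.** 144 participants, 96 intervention and 48 control (SAP, Sample Size; Protocol 27.2); 2:1 allocation within sex and age strata; binomial-logit model; alpha 0.05.

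**Assumptions, because the documents give no figure.** Two-sided test; abstinence rates; two age levels, with sex and age each split 50:50; a standard-normal dependence score; prognostic odds ratios; permuted blocks of 6 (4:2) in four strata; all 144 analysed unless stated.

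**1. The plan's own figure.** The sample size rests on a margin of error of 10% or less at a proportion of 50%. With 1.96 × √(0.25/n):

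- n = 144: 8.2%
- n = 96: 10.0%
- n = 48: 14.1%

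The figure reproduces for the whole sample and the intervention arm, though not for the control arm alone. It describes single proportions and does not depend on the model. There is no power figure to reproduce.

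**2. Arm-only power, closed form, 20% vs 40%.**

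- Pooled proportion = (48 × 0.20 + 96 × 0.40)/144 = 0.333
- Null SE = √(0.333 × 0.667 × (1/48 + 1/96)) = 0.0833
- Alternative SE = √(0.20 × 0.80/48 + 0.40 × 0.60/96) = 0.0764
- Power = Φ((0.20 − 1.96 × 0.0833)/0.0764) = Φ(0.48) = 68.4%

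**3. Adjusted power, same rates.** Simulation, 20,000 trials per scenario, Wald test on arm, Monte Carlo SE about 0.33 points per power figure:

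| Assumed effects (OR: sex, age, dependence per SD) | Arm only | + sex, age | + dependence | Gain, strata | Gain, total |
|---|---|---|---|---|---|
| None | 68.6% | 69.0% | 69.0% | 0.4 | 0.4 |
| Mild (1.5, 1.5, 0.75) | 68.2% | 69.3% | 69.8% | 1.1 | 1.6 |
| Moderate (2, 2, 0.6) | 68.6% | 70.5% | 72.6% | 1.9 | 4.0 |
| Strong (3, 3, 0.5) | 68.6% | 72.8% | 76.5% | 4.2 | 7.9 |

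The arm-only column agrees with step 2.

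**4. Does the gain depend on the test?** At 20% vs 40% it does not. A further 4,000 trials per scenario with a likelihood-ratio test gave:

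- Mild: 70.4/71.5/72.2%, gains 1.1 and 1.8
- Moderate: 70.8/72.9/74.8%, gains 2.1 and 4.0

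A separate likelihood-ratio simulation (3,000 trials, blocks of 3) gave 70.6/71.0/71.1% with no prognostic effect. With stratum ORs of 1.5 and a dependence OR of 2 per SD it gave 70.2/71.3/74.6%. A gain near 10 points (70.9/72.7/80.8%) needed a dependence OR of 3 per SD.

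At 10% vs 25% the test does matter. The total gain (none/mild/moderate/strong) is 1.1/2.1/4.4/7.6 points with Wald and 0.4/1.2/3.1/5.8 with likelihood ratio.

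**5. Type I error, 20% in both arms (none/mild/moderate/strong).**

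| Model | Wald | Likelihood ratio |
|---|---|---|
| Arm only | 4.4/4.4/4.2/3.8% | 5.0/4.9/4.8/4.5% |
| Arm + strata + dependence | 4.8/4.9/4.9/4.9% | 5.2/5.4/5.4/5.6% |

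The arm-only Wald test is already below 5% when nothing is prognostic. A drop due to the omitted strata is clear only in the strong case.

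**6. Precision of the risk difference, 20% vs 40%.** Mean 95% CI width for the three models:

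- None: 29.8/29.9/29.9 points
- Mild: 29.9/29.7/29.4
- Moderate: 29.9/29.3/28.6
- Strong: 29.9/28.6/27.4

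The true variance relative to arm only is 1.00 throughout for the strata, because allocation already balances them. For the full model it is 1.01/1.00/0.96/0.93. Adding the strata makes the stated error match the design. Dependence reduces true variance only if it is at least moderately prognostic.

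**7. Losses.** With 20% lost at random and moderate effects, power is 57.9/60.1/62.6%: gains of 2.2 and 4.7 points.

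**The case against.** This is a pilot sized on feasibility and margin of error, and full efficacy testing is left to a later trial. The unadjusted test is valid and every magnitude above is assumed. Under mild effects the whole gain is about 2 points and the true variance does not change. An interval about 29 or 30 points wide informs the later trial almost equally well. At low abstinence the choice of test matters more than the covariates: arm-only power at 10% vs 25% is 55% with Wald and 63% with likelihood ratio. With about 14 abstainers (10% of 144) a simple model is a reasonable preference.

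All of this stands as to size. It does not remove the point, because the gain appears under both tests, nothing material is lost if no factor is prognostic, and the data are already collected.

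A reader might infer more than the documents support:

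- **That the arm-only analysis is invalid after stratified randomisation.** It is not. Its type I error is at or below about 5% at 20% abstinence.
- **That promised power is lost.** The plan promises none.
- **That silence on covariates leaves room to pick a favourable model.** Always reporting the smallest of the three Wald p-values gives a type I error of only 5.1–6.1% at 20% abstinence.
- **That the dependence measure is undefined.** The survey items are referred to a table and an appendix that are not in the available text, so this cannot be held against the plan.

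**Conclusion.** The point holds as a low-cost efficiency improvement. The stated primary model contains neither the randomisation strata nor baseline dependence, and no other passage adds them. At an assumed 20% vs 40% abstinence, the strata are worth about 1 to 2 points of power. Strata and dependence together are worth about 2 to 4 points for mild to moderate effects, about 8 only as an upper case, and nothing material if none of them predicts quitting. Any conservatism caused by omitting the strata is clear only when they are strongly prognostic; otherwise it mainly reflects a Wald test, which the plan does not specify. The direction of these results is secure. The size rests on assumed rates, age categories and prognostic strength.

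**What to change.** In the SAP (Measures and Statistical Analysis) and Protocol 27.1, replace the model sentence with wording such as:

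*The primary model is a logistic regression of the primary outcome on arm, sex, age (in the categories used for randomisation) and the baseline nicotine-dependence score. The standardised risk difference with 95% CI is reported beside the odds ratio. The arm-only model is a sensitivity analysis. If separation occurs, dependence is dropped and arm plus strata is fitted with a Firth penalty.*

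Name the test (Wald or likelihood ratio) in the same paragraph, and say how a missing dependence score is handled. Setting it to the mean over both arms works: with 10% missing, full-model power under moderate effects was 72.8%, against 72.6% with complete scores. If the team prefers a simpler model, arm plus strata is enough and keeps about half of the gain in the moderate case (1.9 of 4.0 points).

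The cost is one short paragraph and no new data. The downsides are:

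- The odds ratio becomes conditional. At 20% vs 40% the unadjusted value is (0.40/0.60)/(0.20/0.80) = 2.67; with stratum ORs of 1.5 and a dependence OR of 2 per SD the conditional value is 2.96. Its SE is also larger (log-OR SE 0.422 arm only, 0.448 full model, moderate effects). The standardised risk difference keeps an effect measure comparable with the arm-only result.
- With few abstainers the full model is less well behaved. At 10% in both arms, risk-difference coverage is 93.4–94.0% against 94.0–94.3% for arm only, and adjusted likelihood-ratio tests ran slightly above 5% even at 20%.
- Separation at 10% in both arms occurs in 0.9–3.9% of trials with two age groups and 4.5–19.4% with three. The stated fallback keeps the Wald type I error at 3.2–3.7% and 3.4–3.7% respectively.
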